10.1. SAMPLE SIZE CALCULATION

The primary endpoint of this study is the incidence of late pelvic grade ≥ 2 toxicities.

Sample size calculation for the experimental arm (Calypso system) will be based on a single-stage Fleming design for phase II trials. Fleming design is formulated in terms of success rate.

In the context of this study, we define a success as a patient without grade ≥ 2 late pelvic toxicity occurring after 3 months and until 2 years after treatment (based on the Common Terminology Criteria for Adverse Events Version 4.03).

Considering that the common expected success rate in this indication is 85% (p0), the smallest success rate expected in the experimental arm is set at 95% (p1). Using a one-stage Fleming design with one-sided $\alpha=0.05$ and $\beta=0.10$, it will be necessary to include 75 evaluable patients.

Taking into account a 10% rate of non-evaluable patients, a total of 83 patients will be required in Calypso arm.

The number of success will be evaluated on the first 75 evaluable patients.

The experimental treatment (Calypso system) may be considered sufficiently safe if at least 69 patients (among 75 evaluable patients) show a treatment success, otherwise the Calypso system will be considered as insufficiently safe.

Stage	Nb. of patients	Insufficiently safe if	Sufficiently safe if
1	75 first evaluable patients	≤68 successes	≥69 successes

A concurrent control arm of a size equal to half that experimental, that is 38 patients, will be included in the study using a 2:1 randomization ratio (Calypso : Control).

Taking into account a 10% rate of non-evaluable patients, a total of 83 patients will be required in CALYPSO arm whereas 42 patients in Control arm.

Accordingly, **a total of 125 patients will be recruited in the trial**, 83 and 42 patients in Calypso and Control (IGRT) arms respectively.

The control group is used as a validation of the hypothesis that success rate without Calypso system is 85%. The 90% Confidence Interval (90%CI) of the success rate will be estimated on the 38 evaluable patients of the control group. If 85% is included in the 90%CI, the final conclusion will be the Fleming design conclusion. Conversely, if 85% is not included in the 90%CI, the final conclusion will be taken as follows:

IGRT (Control) Group : observed 90%CI	Calypso system : Fleming plan	
	Positive result	Negative result
85% < lower boundary	Discuss the result	Fleming design conclusion
85% within the 90%CI	Fleming design conclusion	Fleming design conclusion
85% > upper boundary	Fleming design conclusion	Discuss the result

Randomisation will be stratified according to the:

- RILA test (low (≤ 15) versus high (> 15)),
- Indication for hormonotherapy (yes versus no),
- Anticoagulation treatment (yes versus no),
- Diabetes patient status (yes versus no)

Note: Sample size is not modified. The proposed change on prescribed dose and fractioning does not alter the original scope of the research as the result of the above cited large non-inferiority trials provide enough evidence of no difference in late pelvic toxicity between normofractionned and moderate hypofractionation. Nonetheless, a subgroup analysis is henceforth planned and a meta-analytic approach will be used to provide a pooled estimation of the proportion of success (and its IC95%) in the experimental Calypso arm (cf. §10.2. Statistical analysis).

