SAMPLE SIZE	
The primary endpoint of this study is the incidence of late pelvic grade ≥ 2 toxicities.
 
Sample size calculation for the experimental arm (Calypso system) will be based on a single-stage Fleming design for phase II trials. Fleming design is formulated in terms of success rate.
 
In the context of this study, we define a success as a patient without grade ≥ 2 late pelvic toxicity occurring after 3 months and until 2 years after treatment (based on the Common Terminology Criteria for Adverse Events Version 4.03).
 
Considering that the common expected success rate in this indication is 85% (p_0), the smallest success rate expected in the experimental arm is set at 95% (p_1). Using a one-stage Fleming design with one-sided $\alpha=0.05$ and $\beta=0.10$, it will be necessary to include 75 evaluable patients.

	
The experimental treatment (Calypso system) may be considered sufficiently safe if at least 69 patients (among 75 evaluable patients) show a treatment success, otherwise the Calypso system will be considered as insufficiently safe.
 
  
 Stage	Nb.of patients	Insufficiently active safe if	Sufficiently active safe if	
   
 1	75 first evaluable patients	≤ 68 successes	≥ 69 successes	
  
 
A concurrent control arm of a size equal to half that experimental, that is 38 patients, will be included in the study using a 2:1 randomization ratio (Calypso : Control).
 
Taking into account a 10% rate of non-evaluable patients, a total of 83 patients will be required in CALYPSO arm whereas 42 patients in Control arm.
 
Accordingly, a total of 125 patients will be recruited in the trial, 83 and 42 patients in Calypso and Control (IGRT) arms respectively.
 
Randomisation will be stratified according to the: Radiation-induced lymphocyte apoptosis (RILA) test (low (≤ 15) versus high (> 15)), Indication for hormonotherapy (yes versus no), Anticoagulation treatment (yes versus no), Diabetes patient status (yes versus no)
				Stage	Nb.of patients	Insufficiently active safe if	Sufficiently active safe if	1	75 first evaluable patients	≤ 68 successes	≥ 69 successes
Stage	Nb.of patients	Insufficiently active safe if	Sufficiently active safe if									
1	75 first evaluable patients	≤ 68 successes	≥ 69 successes									

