10.2. STATISTICAL ANALYSIS

A detailed statistical analysis plan (SAP) will be elaborated before the database is frozen. No formal statistical comparison will be made between the treatment arms.

Data will be summarized using frequencies and percentages for categorical variables and using medians and ranges for continuous variables.

The percentage of patients without grade ≥ 2 late pelvic toxicity (P_{obs}) (success) occurring after 3 months and until 2 years after treatment, as well as the percentage of patients experiencing at least a grade ≥ 2 late pelvic toxicity in that period ($1-P_{obs}$; primary endpoint of the trial) will be presented for each arm with their respective 90% (and 95%) confidence interval based on binomial exact distribution.

The decision about the effect of the experimental arm (Calypso system with reduction of treatment margins) in terms of late pelvic toxicity rate will be stated according the decision rules described in previous section (sample size calculation).

Moreover, in order to control for the additional heterogeneity introduced with the switch to moderate hypofractionation RT we will use a meta-analytic approach in order to consider this factor (i.e. the fractionation-group: normofractionned or moderate hypofractionned) into the calculation of a global pooled proportion of success (and its IC95%) in the experimental Calypso arm.

This analysis will be performed using the Metaprop Stata module, implemented to perform meta-analysis of proportions in the Stata software (References are listed here below). A random effect model will be used to calculate a pooled global estimated of the proportion of success. Metaprop also allows computation of 95%CI using the score statistics and the exact binomial method, and incorporates the Freeman-Tukey double arcsine transformation of proportions. I^2 statistic will be used to describe the percentage of total variation due to the inter fractionation-group heterogeneity. All the details concerning this part of the analysis will be also specified in the SAP [44, 45].

Biochemical and complication relapse-free survival curves will be estimated using the Kaplan-Meier method.

The analysis of QLQ C30 and QLQ PR25 questionnaires will be performed in accordance with the EORTC guidelines.

Specific questionnaires for urinary obstruction (IPSS) and erectile function (IIEF5) will be described at each evaluation and over time.

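### The cut-off of 69 successes in 75 is stated with one-sided alpha 0.05, but its exact alpha is 0.054 (power 0.92); state these rates, and fix one cut-off convention for fewer than 75 evaluable patients

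*Combined protocol and SAP*

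**What the plan says.** Section 10.1 sets the design: "Using a one-stage Fleming design with one-sided" alpha 0.05 and beta 0.10, a null success rate of 85% and an alternative of 95%, giving 75 evaluable patients in the Calypso arm. A success is a patient free of grade 2 or worse late pelvic toxicity from 3 months to 2 years. The rule is "The experimental treatment (Calypso system) may be considered sufficiently safe if at least 69 patients (among 75 evaluable patients) show a treatment success"; 68 or fewer is a negative result. The sample-size part of the synopsis repeats it ("at least 69 patients (among 75 evaluable patients) show a treatment success").

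On numbers, section 10.1 says "The number of success will be evaluated on the first 75 evaluable patients" and "Taking into account a 10% rate of non-evaluable patients, a total of 83 patients will be required in Calypso arm". It then adds a control-arm step. The 90% confidence interval of the control success rate (38 evaluable patients) is compared with 85%. In two cells of the decision table the Fleming result gives way to a discussion: a positive result when 85% lies below the control interval, and a negative result when 85% lies above it.

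Section 10.2 says that the success and toxicity percentages "will be presented for each arm with their respective 90% (and 95%) confidence interval based on binomial exact distribution", and that the decision on the experimental arm "will be stated according the decision rules described in previous section". It defers detail: "A detailed statistical analysis plan (SAP) will be elaborated before the database is frozen". It also reports an analysis in December 2020 with one failure among 35 evaluable Calypso patients, and calls the remaining trade-off between the two errors adequate without giving figures.

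**The concern.** With a binomial count the attained error rates move in steps, so a cut-off taken from a normal approximation seldom meets its nominal alpha exactly. A reader will take 0.05 as the rate that the rule attains. If the exact rate is higher, the plan should say so, because this is the false-positive rate of the count on which the trial's main result turns.

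The second issue is what happens below 75. The rule is defined for 75 patients only, and the recruitment target leaves no slack at the plan's own loss rate. If the count ends at 74 with no convention in place, the cut-off would have to be chosen afterwards. Some outcome data were already examined in December 2020, and one patient could decide the result.

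**Working it through.** **Inputs (section 10.1):** p0 = 0.85, p1 = 0.95, one-sided alpha 0.05 (z = 1.645), beta 0.10 (z = 1.282), n = 75, cut-off 69, 83 recruited, 10% non-evaluable.

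**1. The plan's own figures reproduce.**
- n = [(1.645 × √(0.85 × 0.15) + 1.282 × √(0.95 × 0.05)) / (0.95 − 0.85)]² = [(0.587 + 0.279) / 0.10]² = 75.1, hence 75.
- Boundary at n = 75: 75 × 0.85 + 1.645 × √(75 × 0.85 × 0.15) = 63.75 + 5.09 = 68.84, hence at least 69.

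**2. Exact rates of the count rule,** with X binomial.

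| Rule | Alpha: P(X ≥ r) at 0.85 | Power: P(X ≥ r) at 0.95 |
|---|---|---|
| ≥ 69/75 (plan) | 0.0544 | 0.919 |
| ≥ 70/75 | 0.0234 | 0.828 |

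No cut-off at n = 75 meets both nominal limits: 69 exceeds alpha by 0.0044, and 70 falls short of 90% power by 7 points. Keeping 69 is reasonable.

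**3. The interval at the cut-off.** The exact (Clopper-Pearson) 90% interval for 69/75 is 84.8% to 96.5%, which contains 85%. For 70/75 it is 86.5% to 97.3%, which does not. The chance of exactly 69 successes is 0.03 at a true 85% and 0.09 at 95%.

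**4. Evaluable patients.** Expected number: 83 × 0.90 = 74.7. If exactly 83 are recruited and losses are independent, P(fewer than 75) is 0.22, 0.45 and 0.68 at 8%, 10% and 12% loss. Only the 10% is in the documents. The range shows sensitivity to an assumption and is not an estimate of risk.

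**5. Cut-offs below 75 under two conventions.** A: the Fleming boundary n × 0.85 + 1.645 × √(n × 0.1275), rounded up. B: the smallest r with exact P(X ≥ r) at 0.85 no greater than 0.05.

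| n | Boundary | A: r (alpha, power) | B: r (alpha, power) |
|---|---|---|---|
| 74 | 67.95 | 68 (0.059, 0.92) | 69 (0.026, 0.83) |
| 73 | 67.07 | 68 (0.029, 0.84) | same |
| 72 | 66.18 | 67 (0.032, 0.85) | same |
| 71 | 65.30 | 66 (0.035, 0.86) | same |
| 70 | 64.41 | 65 (0.038, 0.86) | same |
| 69 | 63.53 | 64 (0.042, 0.87) | same |
| 68 | 62.64 | 63 (0.047, 0.88) | same |

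From 68 to 73 both conventions allow at most 5 failures. Within 59 to 74 they differ only at 74 and at 65 to 67. Under the 10% independent-loss assumption, P(exactly 74) = 0.135 and P(67 or fewer) = 0.008. Averaged over the number evaluable on the same assumption, with 69/75 kept, A gives alpha 0.048 and power 0.898; B gives 0.044 and 0.886.

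**The case against.** The plan names its method and quotes alpha and beta as design inputs. A normal-approximation rule with exact size 0.054 is behaving as expected, and its power is above target. That stands against any reading that the sample size was miscalculated. It does not remove the case for stating the attained rates.

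Three stronger readings are tempting, and the documents do not support them.

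- *That 0.054 is the error rate of the trial's final conclusion.* It is the size of the Calypso count rule. The control-arm table can turn a positive count into a discussion. With a true control rate of 85% and 38 patients, 85% falls below the exact 90% interval only at 37 or 38 successes, with probability 38 × 0.15 × 0.85³⁷ + 0.85³⁸ = 0.016. The effect is small, but the two quantities are not the same.
- *That at 69/75 the plan contradicts itself.* The Calypso interval is descriptive, and section 10.2 ties the decision to section 10.1. The only interval with a role in the decision is the control arm's.
- *That a shortfall would push alpha to 0.065–0.084.* Those values arise at n = 70 to 73 only if the boundary is rounded to the nearest integer, which can declare success below the critical value (64 against 64.41). Nothing in the plan suggests this, and 68.84 becoming 69 is consistent with rounding up.

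It is also fair to say that the shortfall rule belongs in an SAP still to be written. That excuses its absence so far and makes this the cheapest time to add it.

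**Conclusion.** The point holds as a correction to what is reported. The count rule's exact one-sided alpha is 0.054 against a stated 0.05, and its exact power is 0.92 against 0.90. The design, the 75 patients and the cut-off of 69 stand. These rates rest only on the plan's p0, p1 and cut-off; they do not measure any effect of the December 2020 analysis.

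The secondary point also holds: 74.7 expected evaluable patients makes a shortfall foreseeable, and the plan has no cut-off for it. Its practical reach is narrow. Under the two natural conventions the cut-off differs by one patient at n = 74, and otherwise, within 59 to 74, only at 65 to 67. A reader might infer that the stricter exact limit is required. It is not: it lowers alpha at 74 from 0.059 to 0.026 but costs about 9 points of power, and the plan already accepts 0.054 at 75. What matters is that one convention is fixed in advance. If 75 or more patients are evaluable, only the reporting point remains.

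**What to change.** 1. In section 10.1 and the synopsis, keep 75 and at least 69, and add: *Under the exact binomial distribution the Calypso count rule has one-sided alpha 0.054 at 85% and power 0.92 at 95%, before the control-arm check in the decision table.*
2. A note on the interval is optional. If one is added, it should say only that at 69/75 the descriptive exact 90% interval (84.8% to 96.5%) contains 85% while the Fleming result is positive, and that the final conclusion remains subject to the control-arm table.
3. In the SAP, before database freeze and before the final count is known, add one sentence fixing the cut-off for fewer than 75 evaluable patients from the original 85% and 0.05: either the Fleming boundary rounded up, or the smallest count with exact alpha no greater than 0.05. State that the choice does not draw on the December 2020 data.

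The cost is one sentence in two places and one in the SAP. The 125 patients and the 69/75 cut-off do not change. Under either convention, power is below 0.90 for 68 to 73 evaluable patients (0.84 to 0.88); at 74 it is 0.92 or 0.83, depending on the convention.

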10.2. STATISTICAL ANALYSIS

A detailed statistical analysis plan (SAP) will be elaborated before the database is frozen. No formal statistical comparison will be made between the treatment arms.

Data will be summarized using frequencies and percentages for categorical variables and using medians and ranges for continuous variables.

The percentage of patients without grade ≥ 2 late pelvic toxicity (P_{obs}) (success) occurring after 3 months and until 2 years after treatment, as well as the percentage of patients experiencing at least a grade ≥ 2 late pelvic toxicity in that period ($1-P_{obs}$; primary endpoint of the trial) will be presented for each arm with their respective 90% (and 95%) confidence interval based on binomial exact distribution.

The decision about the effect of the experimental arm (Calypso system with reduction of treatment margins) in terms of late pelvic toxicity rate will be stated according the decision rules described in previous section (sample size calculation).

Moreover, in order to control for the additional heterogeneity introduced with the switch to moderate hypofractionation RT we will use a meta-analytic approach in order to consider this factor (i.e. the fractionation-group: normofractionned or moderate hypofractionned) into the calculation of a global pooled proportion of success (and its IC95%) in the experimental Calypso arm.

This analysis will be performed using the Metaprop Stata module, implemented to perform meta-analysis of proportions in the Stata software (References are listed here below). A random effect model will be used to calculate a pooled global estimated of the proportion of success. Metaprop also allows computation of 95%CI using the score statistics and the exact binomial method, and incorporates the Freeman-Tukey double arcsine transformation of proportions. I^2 statistic will be used to describe the percentage of total variation due to the inter fractionation-group heterogeneity. All the details concerning this part of the analysis will be also specified in the SAP [44, 45].

Biochemical and complication relapse-free survival curves will be estimated using the Kaplan-Meier method.

The analysis of QLQ C30 and QLQ PR25 questionnaires will be performed in accordance with the EORTC guidelines.

Specific questionnaires for urinary obstruction (IPSS) and erectile function (IIEF5) will be described at each evaluation and over time.

Subgroup analysis: a subgroup analysis into the experimental arm (Calypso system) will be conducted between the subgroup of patients that have followed a conventional RT and those who have followed a hypofractionned RT. This analysis concerns mainly the primary endpoint as well as toxicity-related secondary endpoints.

All statistical analyses will be performed with the Stata v16 software (StataCorp LP, College Station, TX).

Note: previous to the present protocol modification, an analysis was conducted on December 2020, focussed on the incidence of pelvic late grade ≥ 2 toxicity. This analysis based on 35 evaluable patients in Calypso system (24 evaluable in RTGI standard) revealed only two failures overall, one in each group.

Despite of this interim analysis, the planned sample size in this phase 2 trial (non-comparative) still large enough for a final analysis with an adequate final trade-off between α and β errors.

Statistical reports planned:

According to estimated study duration (Paragraph § 2.2):

The final statistical analysis is planned at the end of 2028 (end of inclusions planned for April 2026) including primary and secondary endpoints with a minimal median follow-up of 5 years. A statistical report will be delivered at that occasion.

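### Random-effects pooling of two fixed fractionation groups can give a misleadingly wide 95% CI for the Calypso success proportion if the regimens differ

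*Combined protocol and SAP*

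**What the plan says.** The note at the end of section 10.1 says that, after the change of fractionation, "a meta-analytic approach will be used to provide a pooled estimation of the proportion of success (and its IC95%) in the experimental Calypso arm". Section 10.2 names the groups to be pooled ("i.e. the fractionation-group: normofractionned or moderate hypofractionned") and the target, a "global pooled proportion of success (and its IC95%) in the experimental Calypso arm". It then fixes the model, "A random effect model will be used to calculate a pooled global estimated of the proportion of success", and adds that the I-squared "statistic will be used to describe the percentage of total variation due to the inter fractionation-group heterogeneity". Freeman-Tukey transformation, score intervals and exact intervals are mentioned as features of the Stata command. Further detail is left to the SAP.

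Three other statements in section 10.2 bear on the point. The success and failure percentages "will be presented for each arm with their respective 90% (and 95%) confidence interval based on binomial exact distribution". The decision on Calypso follows the Fleming rule of section 10.1 (at least 69 successes in 75). And "a subgroup analysis into the experimental arm (Calypso system) will be conducted between the subgroup of patients that have followed a conventional RT" and those given hypofractionated treatment.

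**The concern.** A random-effects model treats the units pooled as draws from a wider population and estimates that population's mean. Here there are two units, they are fixed and exhaustive, individual data are held on every patient, and the quantity wanted is the arm's own success proportion. The between-group variance and I-squared rest on one degree of freedom. If the two groups differ visibly, the interval reports the gap between regimens instead of how precisely the arm's proportion is known.

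At stake is the reading of the result. Two 95% intervals for the same arm would be reported, one of them presented as the control for the fractionation switch, and no sentence ranks them. I-squared would be offered as the description of regimen heterogeneity although it is too unstable with two groups to serve.

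**Working it through.** **The plan's own figure.** The plan gives no number for the pooled estimate. The design it sits beside reproduces. With p0 = 0.85, p1 = 0.95, one-sided alpha 0.05 and beta 0.10, n = [(1.645·√0.1275 + 1.282·√0.0475)/0.10]² = 75.1. The threshold is 75·0.85 + 1.645·√(75·0.1275) = 68.8, hence 69 of 75.

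**Inputs and assumptions.** There are 75 evaluable Calypso patients (section 10.1). Section 10.2 reports for December 2020: "This analysis based on 35 evaluable patients in Calypso system (24 evaluable in RTGI standard) revealed only two failures overall, one in each group", so 34/35 in Calypso before the switch. The final split is not given; 35/40, 45/30 and 55/20 are assumed. The variance estimator and scale are not fixed; a moment estimator on the Freeman-Tukey scale is assumed, back-transformed at the harmonic mean of the group sizes.

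**Why the width ignores sample size.** Let tᵢ = arcsin√(xᵢ/(nᵢ+1)) + arcsin√((xᵢ+1)/(nᵢ+1)), vᵢ = 1/(nᵢ+0.5) and d = t₁ − t₂. With two groups:

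- τ² = max(0, d²/2 − (v₁+v₂)/2). DerSimonian-Laird, Hedges-Olkin, Paule-Mandel and REML all give this value.
- When τ² > 0, SE² = d²/4 − (v₁−v₂)²/(4d²), which is close to d²/4. The half-width is then about 1.96·|d|/2 = 0.98·|d|.

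**Worked example, 34/35 and 34/40.** t₁ = 2.736, t₂ = 2.323, d = 0.413; v₁ = 0.0282, v₂ = 0.0247. τ² = 0.0853 − 0.0264 = 0.0589. SE = 0.2065, against d/2 = 0.2066. Back-transformed, the interval is 76.8–99.8%. The exact interval on 68/75 is 81.7–96.2%.

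**Other outcomes with 34/35 in the first group:**

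| Second group | Total | Random effects 95% CI | Exact 95% CI |
|---|---|---|---|
| 34/40 | 68/75 | 76.8–99.8% | 81.7–96.2% |
| 35/40 | 69/75 | 81.1–99.5% | 83.4–97.0% |
| 38/40 | 72/75 | 89.9–99.7% | 88.8–99.2% |

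As an illustration of the formula only, ten times the patients at the proportions in the first row leaves the random-effects width at 0.232, while the exact width falls from 0.145 to 0.043.

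**Expected widths, by full enumeration of the binomial outcomes:**

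| Split | True rates | Mean width, random effects | Mean width, exact | Coverage, random effects / exact |
|---|---|---|---|---|
| 35/40 | 95%, 95% | 0.114 | 0.110 | 0.969 / 0.966 |
| 35/40 | 97%, 93% | 0.126 | 0.111 | 0.974 / 0.967 |
| 35/40 | 97%, 90% | 0.163 | 0.124 | 0.964 / 0.984 |
| 35/40 | 97%, 85% | 0.237 | 0.143 | 0.991 / 0.959 |
| 45/30 | 97%, 85% | 0.238 | 0.132 | 0.985 / 0.974 |
| 55/20 | 97%, 85% | 0.240 | 0.120 | 0.980 / 0.978 |

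Coverage is for the size-weighted arm proportion. The point estimate itself moves little: at 97% and 85% the mean absolute shift from the observed proportion is at most 1.7 points over the three splits.

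**I-squared at 35/40.** It exceeds 50% in 21% of trials when both rates are 95%, and is 0% in 19% of trials when the rates are 97% and 85%.

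**The case against.** - **The effect needs a real gap.** Section 10.1 expects no difference in late pelvic toxicity between regimens. At a four-point gap the excess width is small (0.126 against 0.111), and with 37/40 or 38/40 in the second group the random-effects interval is slightly narrower than the exact one. This stands, and the concern is limited to the case where the regimens differ. But handling such a difference is the reason section 10.2 gives for adding the analysis.
- **The clearest example, 68/75, already fails the Fleming rule.** True. At 97% and 85% with a 35/40 split, only 43% of trials reach 69; among those the mean widths are 0.176 against 0.124. The excess is smaller but remains.
- **The lower limit depends on the scale.** For 34/35 and 35/40 on the untransformed scale the interval is 84.1–102.6%, so the lower limit is above the exact 83.4% and the excess lies at the top. This stands for that outcome. For 34/35 and 34/40 the untransformed interval is 80.3–103.8%, as wide as on the Freeman-Tukey scale (0.235 against 0.230).
- **A wider interval is conservative.** Only in part. The exact interval already covers adequately, and at 97% and 90% the random-effects interval is wider on average yet covers less often (0.964 against 0.984).
- **The hierarchy is clear and the SAP will settle details.** The order of section 10.2 does suggest that the exact interval comes first, though no sentence says so. The SAP is left the details, but the protocol has already fixed the model, and the usual variance estimators coincide for two groups.

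**Conclusion.** The concern holds as a conditional point. The model does not fit its stated target, and if the regimens differ the pooled 95% CI is misleadingly wide: about 1.3 times the exact width at true rates of 97% and 90% (0.163/0.124), and 1.7 to 2.0 times at 97% and 85% (0.237/0.143 to 0.240/0.120). If they share one rate, little is lost. These figures rest on 75 evaluable patients, the assumed splits, the Freeman-Tukey scale and a moment estimator. The result for the standard error holds for any split and for the four estimators named.

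The consequence is limited to a supplementary estimate. The 69-of-75 decision and the exact intervals for each arm do not change. It is worth considering because it can be corrected before the final data are seen.

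**What to change.** In section 10.2, delete the random-effects and I-squared sentences; in section 10.1, delete the reference to meta-analysis. State that the observed Calypso success proportion, with its already planned exact binomial 95% CI, is the single pooled estimate. It equals the size-weighted mean of the two groups (for example 35/75·34/35 + 40/75·34/40 = 68/75 = 90.7%), so no fractionation-weighted estimate is lost.

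In the planned subgroup analysis, name the statistics: each regimen's success proportion with exact 95% CI, and the difference between regimens with a Newcombe 95% CI, labelled descriptive. For 34/35 and 34/40 this gives 97.1% (85.1–99.9%), 85.0% (70.2–94.3%) and a difference of 12.1 points (−2.0 to 26.4).

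The cost is wording in sections 10.1 and 10.2 and in the SAP, with no new data and no change to sample size or decision rule. The regimen difference will be imprecise, about 28 points wide in the example, but that uncertainty is real and I-squared would hide it.
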